9.4 Confirmatory measurement/duration of response

- 9.4.1 Confirmation: To be assigned a status of PR or CR, changes in tumor measurements must be confirmed by repeat assessments that should be performed four weeks after the criteria for response are first met. In the case of SD, follow-up measurements must have met the SD criteria at least once after study entry at a minimum interval of eight weeks.
- 9.4.2 Duration of overall response: The duration of overall response is measured from the time measurement criteria are met for CR or PR (whichever is first recorded) until the first date that recurrent or progressive disease is objectively documented (taking as reference for progressive disease the smallest measurements recorded since the treatment started). The duration of overall CR is measured from the time measurement criteria are first met for CR until the first date that recurrent disease is objectively documented.
- 9.4.3 Duration of stable disease: Stable disease is measured from the start of the treatment until the criteria for progression are met, taking as reference the smallest measurements recorded since the treatment started.

Safety and Immunologic Activity of Multiple Infusions of APN401
Wake Forest Baptist Comprehensive Cancer Center
CCCWU 03716

10.0 Laboratory Correlates

10.1 Sample collection

Peripheral blood will be obtained at baseline prior to the first infusion, on day 29 and 57 (four and eight weeks after the infusion) and every eight weeks thereafter. Twenty (20) ml of blood is collected in two 10ml EDTA-containing vacutainers and sent to [name] laboratory, [name].

10.2 Immune Response Outcomes

All research laboratory procedures will be performed per manufacturer's recommendations with amendments (if needed) as necessary to adapt the protocol to the current applications. Procedures and results will be recorded in a laboratory notebooks but also recorded on Appendices L through N.

10.2.1 PMBC IFNy production in vitro (R&D Systems ELISA) in response to anti-CD3 plus anti-CD28 antibody (BD) (Appendix L)

10.2.2 PMBC IFNy production in vitro (R&D Systems ELISA) in response NY-ESO, survivin, and telomerase peptide mixtures (Proimmune Promix) (Appendix L)

10.2.3 Frequency (flow cytometry) of CD4+, CD8+, CD4+FoxP3+ regulatory, ICOS+CD4+ and ICOS+CD8+ effector, and CD45RO+CD4+ memory T cells and CD3-CD56+ NK cells and CD19 B cells (Appendix M)

10.2.4 Neutrophil to lymphocyte ratio (Appendix N)

11.0 Statistical Considerations

11.1 Study Outcomes

11.1.1 Primary Outcome

- Rate of Toxicities when patients are administered APN401 for one year

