MAIN INCLUSION CRITERIA	
 Signed written informed consent Histologically confirmed metastatic or inoperable solid tumor no longer responding to standard therapies Must be at least 4 weeks since prior systemic therapy, radiation and/or surgery ECOG performance status 0-1 Hematocrit $\geq 28\%$, WBC $>3000/\mu\text{l}$, and platelets $>100,000/\mu\text{l}$ Creatinine $\leq 1.6 \text{ mg/dl}$ ALT and AST <2.5 fold the upper limit of normal and total bilirubin $\leq 1.6 \text{ mg/dl}$
MAIN EXCLUSION CRITERIA	
 Pregnant or breastfeeding patients Untreated, progressing, or symptomatic brain metastasis HIV, hepatitis B, or hepatitis C (active) infection Active autoimmune disease Ongoing requirement for an immunosuppressive treatment Significant cardiovascular or pulmonary disease
TREATMENT PLAN	
 PBMC for infusions will be collected by leukapheresis the day prior to infusion. Patients will be administered three infusions separated by 4 weeks Blood will be drawn pre-therapy and at 3, 5, 9, and 10 weeks, and then every 8 weeks for immune assessments Imaging will be performed pre-therapy and 2 weeks after infusion 3 and then every 8 weeks for clinical response Six patients will be treated initially. If a dose limiting toxicity (DLT) is observed in $\leq 1/6$, than an additional four patients will be enrolled to allow evaluation of laboratory correlates. Enrollment will be suspended if $>1/6$ or $>3/12$ patients manifest DLT
LABORATORY CORRELATES	
 PBMC cytokine response Circulating immunocytes
POPULATION SIZE	
 Two to 12 eligible and evaluable patients
STUDY DURATION	
 Patients will be followed for toxicity until objective disease progression or 1 year, whichever occurs first.

Safety and Immunologic Activity of Multiple Infusions of APN401
Wake Forest Baptist Comprehensive Cancer Center
CCCWU 03716

Contents

1.0	Background	6
1.1	Adoptive cellular immunotherapy	6
1.2	Cbl-b	6
1.3	APN401	7
1.4	Phase 1 study of single infusion of APN401	7
1.5	Study rationale	7
2.0	Objectives	8
2.1	Primary	8
2.2	Secondary	8
3.0	Selection of Patients	8
3.1	Inclusion criteria	8
3.2	Exclusion criteria	9
4.0	Patient Registration	10
5.0	Treatment Plan	11
5.1	Dosing	11
5.2	Leukapheresis	11
5.3	Infusion	11
5.4	Supportive care guidelines	12
5.5	Nursing implications	13
5.7	Duration of follow-up	14

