5.0 Treatment Plan

5.1 Dosing

- 5.1.1 Leukapheresis to collect PBMC for infusion will be performed the day prior to infusion. Patients will be administered three infusions of APN401 at 50×10^6 cells/kg IV, separated by 4 weeks (reference Appendix I). Leukapheresis and administration of APN401 can be delayed up to 3 weeks at the physician's discretion. Subsequent treatment must occur 28 days after prior treatment.
- 5.1.2 Six patients will be treated initially. Should >1/6 subjects experience greater than grade 3 or 4 toxicity, further enrollment of study subjects and further administration of the study agent will stop pending assessment of the risk.
- 5.1.3 If DLT is observed in $\leq 1/6$, than an additional four patients (a total of 12) will be enrolled to allow evaluation of laboratory correlates. Enrollment will be suspended if >1/6 or >3/12 patients manifest DLT

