5.7 Duration of follow-up

All patients, including those who discontinue protocol therapy early, will be followed for response until progression or one year from registration, whichever occurs first. Patients will then be followed for survival for five years from the date of registration. All patients must also be followed through completion of all protocol therapy.

Safety and Immunologic Activity of Multiple Infusions of APN401
Wake Forest Baptist Comprehensive Cancer Center
CCWFU 03716

6.0

Study Calendar

Baseline evaluations, including imaging, are to be conducted within 4 weeks prior to initiation of treatment (Day 0). In the event that the patient's condition is deteriorating, laboratory evaluations should be repeated within 48 hours prior to initiation of the next cycle of therapy.

		Treatment Phase							Follow-Up Phase		Early Termination
	Pre-Study ^J	Day 0 Week 1	Day 1 Week 1	Day 15 Week 3 (± 1 day)	Day 28 Week 5 (± 3 days)	Day 29 ^N Week 5	Day 56 Week 9 (± 3 days)	Day 57 ^N Week 9	Day 71 Week 10 (± 3 days)	Week 18 and every 8 weeks (± 1 week) ^L	Off Study Visit/Early Termination Visit ^{L,M}
Leukapheresis ^A		X			X		X				
APN401 ^B			X			X		X			
Informed consent	X										
Demographics	X										
Medical history	X										
Concurrent meds		X			X		X		X	X ^O	X
Vital signs ^C	X	X	X	X	X	X	X	X	X	X	X
Physical exam ^Q	X	X		X	X		X		X	X	X
Performance status	X	X		X	X		X		X	X	X
CBC w/diff ^D	X	X		X	X		X		X	X	X
Chemistries ^E	X	X		X	X		X		X	X	X
PT, PTT	X										
HIV, HBV, HCV	X										
βhCG ^F	X										
Adverse events		X	X	X	X	X	X	X			X
Imaging ^G	X								X ^L	X ^K	X ^L
Tumor marker ^H	X								X	X	X
Immune response ^I		X		X	X		X			X	X

A. PBMC will be harvested from the peripheral blood by a standard 1.5 to 2.0 blood volume mononuclear cell leukapheresis.

B. APN401 is infused 50 x10⁵/kg IV over 30 minutes

C. Vitals signs should include blood pressure, heart rate, temperature, and respiratory rate. At the administration visits, vital signs should also be performed before infusion and 30 and 60 minutes after the end of the infusion.

D. Hemoglobin, hematocrit, white blood cell count, and platelets. The CBC differential includes enumeration of neutrophils, lymphocytes, eosinophils, monocytes, basophils and any abnormal blood cells.

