M. Off study/early termination assessments are only indicated for patients who do not complete all study visits (until week 58) /Follow-Up phase. These assessments should occur no more than 4 weeks after the discontinuation of study treatment. If the subject had not undergone imaging within the past 6 weeks re-imaging is indicated. If a patient discontinues treatment for any reason other than progression, imaging will be done every 12 weeks until progression.

N. Must occur the day following leukapheresis day.

O. Following the week 18 visit only documentation of anti-cancer treatment.

P. Adverse events will be recorded on an ongoing basis and up to 2 months following the administration of the test drug.

Q. Physical Exam may be completed +/- 2 days of visit.

Safety and Immunologic Activity of Multiple Infusions of APN401
Wake Forest Baptist Comprehensive Cancer Center
WFBCCC 03716

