8.0 Toxicity Criteria and Adverse Event Reporting

8.1 Adverse event definition

An adverse event is any physical or clinical change or disease experienced by the subject at any time during the course of the study, whether or not considered related to the use of the study drug. This includes the onset of new illness and the exacerbation of pre-existing

Safety and Immunologic Activity of Multiple Infusions of APN401
Wake Forest Baptist Comprehensive Cancer Center
CCCWU 03716

conditions. Disease-related symptoms that do not increase in severity or frequency from baseline are not considered adverse events.

All toxicity should be graded according to the NCI Common Terminology Criteria for Adverse Events (CTCAE) version 4.0. Adverse events will be recorded on an ongoing basis and up to 2 months following the administration of the test drug. All appropriate treatment areas should have access to a copy of the CTCAE version 4.0. A copy of the CTCAE version 4.0 can be downloaded from the CTEP web site (<http://ctep.cancer.gov>).

- **‘Expectedness’:** AEs can be ‘Unexpected’ or ‘Expected’ (see Section 7.3 above) for expedited reporting purposes only.

- **Attribution** of the AE:

Definite – The AE **is clearly related** to the study treatment.

Probable – The AE **is likely related** to the study treatment.

Possible – The AE **may be related** to the study treatment.

Unlikely – The AE **is doubtfully related** to the study treatment.

Unrelated – The AE **is clearly NOT related** to the study treatment.

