8.2 Dose limiting toxicity (DLT)

DLT is defined as

- 8.2.1 CTCAE grades 3-5 allergic reactions related to study cell infusion
- 8.2.2 CTCAE grades 3 and greater autoimmune reactions other than that vitiligo
- 8.2.3 CTCAE grades 3 and greater organ toxicity (cardiac, dermatologic, gastrointestinal, hepatic, pulmonary, renal/genitourinary or neurologic) not pre-existing or due to the underlying malignancy and occurring within 30 days of study product infusion
- 8.2.4 Treatment-related death within 8 weeks of the study cell infusion

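### The assessment period for the primary toxicity outcome is stated inconsistently across section 11.1.1, the synopsis, section 8.1 and the Study Calendar

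*Combined protocol and SAP*

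**What the plan says.** Section 11.1.1 gives the primary outcome as "Rate of Toxicities when patients are administered APN401 for one year". The synopsis sets the dosing: "Patients will be administered three infusions separated by 4 weeks". The Study Calendar (section 6.0) places the infusions on Days 1, 29 and 57. Section 5.1.1 adds that "Leukapheresis and administration of APN401 can be delayed up to 3 weeks at the physician's discretion".

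The period over which toxicity is observed is described in several places:

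- Synopsis, study duration: "Patients will be followed for toxicity until objective disease progression or 1 year, whichever occurs first".
- Section 8.1, repeated in calendar note P: "Adverse events will be recorded on an ongoing basis and up to 2 months following the administration of the test drug". Neither says which infusion starts the 2 months.
- Study Calendar: the row "Adverse events" is marked at Days 0, 1, 15, 28, 29, 56 and 57 and at the off-study/early-termination visit. It is blank at Day 71 and from Week 18.
- Calendar note M: "Off study/early termination assessments are only indicated for patients who do not complete all study visits (until week 58) /Follow-Up phase". That visit is due no later than 4 weeks after study treatment stops.
- Section 5.7: the limit of progression or one year is attached to response, not toxicity.

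Section 8.2 sets the periods that the DLT count needs. Organ toxicity counts within 30 days of an infusion, and the fatal category is "Treatment-related death within 8 weeks of the study cell infusion". The allergic and autoimmune categories have no time limit.

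**The concern.** Safety of multiple infusions is the sole primary objective in section 2.1, yet the plan does not fix the period over which its outcome is counted. The statements cannot all be followed: no patient receives APN401 for a year, and recording that ends 2 months after an infusion does not give a one-year rate.

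The third infusion matters most. It is the furthest step beyond the earlier single-infusion study, and its follow-up is the part that changes with the passage a site applies. Ascertainment may also depend on disease course, because early leavers have an adverse-event-marked visit after stopping and patients who complete all visits do not. Events that go unrecorded lower the counts used against the 1/6 and 3/12 limits, whether these are read as DLTs (section 5.1.3) or as grade 3-4 toxicity (section 11.4.1). The error would always favour calling the product tolerable.

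**Working it through.** **Windows for a nominal third infusion on Day 57 (calendar; section 8.2)**

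- 30-day organ-toxicity window: 57 + 30 = Day 87.
- 8-week window for treatment-related death: 57 + 56 = Day 113.

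**Recording period under each reading**

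- Section 8.1 counted from the last infusion: 57 + 60 or 61 = Day 117-118. Both timed windows are covered. Against a one-year outcome this is 118/365 = 32%.
- Section 8.1 counted from the first infusion: 1 + 60 or 61 = Day 61-62. This is 4-5 days after infusion 3, so most of both windows is lost.
- Synopsis rule with progression on the Day 71 (± 3 days) scan: follow-up ends on Day 68-74, which is 11-17 days after infusion 3 and 13-19 days before Day 87.
- Calendar marks, patient completing all visits: the last marked visit is Day 57.
- Calendar marks, early leaver after infusion 3: the off-study visit falls by 57 + 28 = Day 85 if stopping is counted from Day 57, two days short of Day 87.

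Dosing spans 57/365 = 16% of a year. If infusions 2 and 3 were each delayed by 3 weeks (an assumption about how section 5.1.1 applies), the last infusion would fall on Day 57 + 42 = Day 99 and its windows would move with it. The period therefore has to be tied to the last infusion received, not to a calendar day.

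**The plan's own stage 1 figures (section 11.4.1)**

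P(more than 1 of 6) = 1 − (1 − p)^6 − 6p(1 − p)^5.

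- p = 0.10: 1 − 0.5314 − 0.3543 = 0.1143. The plan states 11.4%.
- p = 0.40: 1 − 0.0467 − 0.1866 = 0.7667. The plan states 76.7%.

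Both reproduce. They presume that every qualifying event is recorded.

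**Illustration of under-recording**

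Assume a true rate of 40% over three infusions, with equal and independent risk at each.

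- Risk per infusion: 1 − 0.6^(1/3) = 0.1566.
- Rate from infusions 1 and 2 alone: 1 − (1 − 0.1566)^2 = 0.2886.
- Added by infusion 3: 0.40 − 0.2886 = 0.1114.

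| Share of infusion-3 events missed | Apparent rate | P(more than 1 of 6) |
|---|---|---|
| None | 0.400 | 76.7% |
| A quarter | 0.2886 + 0.75 × 0.1114 = 0.372 | 72.1% |
| Half | 0.2886 + 0.5 × 0.1114 = 0.344 | 67.0% |
| All | 0.289 | 55.5% |

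The documents give no missed share. The last row is an extreme bound, not an expectation.

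**The case against.** The strongest answer is that section 8.1 already does the work. It requires ongoing recording, its natural reading runs from the last infusion, and on that reading both timed DLT windows are covered. Nothing says that the calendar or the synopsis overrides it. This stands as far as it goes, but the text does not name the infusion, and the synopsis expressly ends toxicity follow-up at progression.

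A reader might infer from the calendar that no adverse-event assessment is scheduled after Day 57. The documents do not support that. The off-study visit carries a mark, and section 8.1 and note P apply between visits. Physical examination, blood count and chemistries are also scheduled at Day 71 and from Week 18, so many toxicities could still be seen. In addition, note P has no marker in the calendar as extracted, whereas the other notes do. A marker may have been lost, so the blank cells should be checked against the original page.

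Safety reporting is a partial backstop. Unexpected grade 4 and all grade 5 events up to 30 days after last treatment go to the institutional safety committee (Appendix C), as do grade 3-5 infusion reactions (section 8.3). A grade 3 organ toxicity that is not an infusion reaction is a DLT under section 8.2.3 but need not be reported there.

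Finally, the one-year phrase may be a misplaced modifier meaning a year of observation. Section 11.1.2 uses it that way for immune monitoring. That is plausible, and it would bring section 11.1.1 close to the synopsis. The conflict with the 2-month limit on recording would remain.

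**Conclusion.** The inconsistency is real and should be corrected, because it leaves the primary outcome without a defined assessment period. A year of administration contradicts the dosing schedule. A year of observation contradicts the 2-month recording limit, which reaches about 32% of a year at best. Two permissible readings (2 months from the first infusion, or stopping at progression on the Day 71 scan) end toxicity follow-up before the 30-day window of infusion 3 closes.

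Two stronger conclusions are tempting and do not hold. A reader might say that the outcome cannot be measured. That is true only of the literal wording about a year of administration, and a toxicity rate over a stated window is measurable. A reader might also say that third-infusion DLTs will be missed. That depends on which passage is followed, and it does not follow for the timed DLTs if section 8.1 is counted from the last infusion.

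Any under-recording would bias the 1/6 and 3/12 counts towards tolerability, by an unknown amount. The range of 72.1% to 55.5%, against the planned 76.7%, rests on an assumed 40% true rate, equal risk per infusion and assumed missed shares. The lower end ignores ongoing recording, examinations, laboratory tests and safety reporting.

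**What to change.** Reconcile the synopsis, the Study Calendar and its notes, section 8.1 and section 11.1.1 to one toxicity window:

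- Restate section 11.1.1 as the rate of toxicities from the first infusion until 2 months after the last infusion received.
- State in section 8.1 and note P that the 2 months run from the last infusion received.
- Make clear, in the synopsis as well, that adverse-event recording continues through this window after progression or early stopping.
- Mark adverse events at the existing Day 71 and Week 18 visits.

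The cost is small: wording changes, two calendar marks at visits that already include examination and laboratory tests, some extra data collection, and at most a telephone contact for patients who leave early. The reported toxicity rate may be slightly higher.

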11.1.2 Secondary Outcome

- To determine the immunologic effects of multiple infusions of APN401 through monitoring immune response in vitro by measuring IFN production, frequency of immune cells, and neutrophil to lymphocyte ratio for one year.
- To document clinical response and survival using from RECIST criteria and progression free survival and overall survival for five years, respectively.

11.1 Study parameters

The primary goals are to determine the toxicities and to determine effects on immune response. The secondary goal is to document clinical effects.

Safety and Immunologic Activity of Multiple Infusions of APN401
Wake Forest Baptist Comprehensive Cancer Center
CCCWU 03716

11.2 Sample size

A total of up to 12 patients will be treated to allow evaluation of laboratory correlates.

11.3 Analyses

11.3.1 Study parameters

The primary goal of this study is to estimate the rate of toxicities. The secondary goals include determining the effects of treatment on immune response and also to examine clinical effects (response (from RECIST criteria), progression free survival and overall survival)

11.3.2 Sample size

A total of up to 12 patients will be treated to allow evaluation of laboratory correlates. The design allows for an interim analysis to occur after the first 6 patients are enrolled. If 1 or less experience a grade 3-4 toxicity then 4 more will be enrolled, if 3 or less experience a grade 3-4 toxicity the agent will not be considered too toxic. With this sample size, during the first stage of the trial, if the true toxicity rate is 10% (or less) the trial will stop with 11% probability, whereas if the true toxicity rate is 40% (or higher) then the trial will stop with 76.7% probability. Likewise, if the trial continues to 12 patients, if the true toxicity rate is 10% or less the probability of observing more than 3 toxicities is 1.2% and if the true toxicity rate is 40% or more then the probability of observing more than 3 toxicities is 62%.

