11.4 Analyses

Adverse events will be categorized by organ system and severity and summarized as frequency counts and percentages. Other categorical data, such as clinical response, will be summarized similarly. Measured data, such as immune response, will be summarized as medians and ranges. All tests of statistical significance will be 2-sided and p-values will generally not be adjusted for multiple comparisons.

11.4.1 **Toxicity:** APN401 will be considered tolerable if $\leq 1/6$ or if overall $\leq 3/12$ patients (i.e. an observed toxicity rate of at most 30%) experience grade 3-4 toxicity. With this design the likelihood of stopping early and rejecting the therapy as too toxic is $\leq 11.4\%$ if the true grade 3-4 toxicity rate is $\leq 10\%$ and $> 76.7\%$ if it is $> 40\%$. The overall likelihood of declaring APN401 too toxic is $\leq 1.2\%$ and $> 62\%$, respectively in these scenarios.

11.4.2 **Immune response:** APN401 will be considered immunologically active if PBMC IFN- γ production in response to anti-CD3/28 stimulation or to one or more tumor antigens is significantly increased or if neutrophil to lymphocyte ratio is significantly decreased post-therapy (week 9) compared to pre therapy. Immune responses will be summarized as medians and ranges. The effects of treatment on these markers individually will be analyzed using paired t-tests or the non-parametric counterpart. With 12 patients there will be statistical power equal to 80% to detect 1 standard deviation change in these markers following treatment. All tests will be 2-sided and $P < 0.05$ will be considered significant.

Safety and Immunologic Activity of Multiple Infusions of APN401
Wake Forest Baptist Comprehensive Cancer Center
CCCWU 03716

11.4.3 Clinical response and survival: Clinical response will be assessed by RECIST and summarized as frequency counts and percentages. Progression-free survival and overall survival are calculated from the initial infusion to confirmation of progression or death. Exploratory survival plots will be estimated using the Kaplan Meier approach and median PFS and OS will be estimated if enough events occur.

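### The toxicity rule enrols 6 + 4 patients but calls the total 12, and its overall rejection probabilities (1.2% and 62%) lie below its own early-stopping probabilities

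*Combined protocol and SAP*

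**What the plan says.** - **Enrolment.** Section 11.3.2 places an interim look after the first six patients and then says: "If 1 or less experience a grade 3-4 toxicity then 4 more will be enrolled". Section 5.1.3 says "an additional four patients (a total of 12) will be enrolled to allow evaluation of laboratory correlates". The synopsis also adds four to six. Sections 11.2 and 11.3.2 give a maximum of 12, and the final boundary in the synopsis, 5.1.3 and 11.4.1 is written over 12 (suspend if more than 3/12; tolerable if at most 3/12).
- **First stage.** Sections 11.3.2 and 11.4.1 give the probability of stopping after six patients as 11% (11.4%) at a true toxicity rate of 10% and 76.7% at 40%.
- **Final stage.** For a trial that continues to 12, section 11.3.2 states "if the true toxicity rate is 10% or less the probability of observing more than 3 toxicities is 1.2"%, and 62% at a true rate of 40%. Section 11.4.1 introduces the same two numbers with "The overall likelihood of declaring APN401 too toxic is".
- **Related figures.** Section 11.4.1 describes 3/12 as "an observed toxicity rate of at most 30"%. Section 11.4.2 says "With 12 patients there will be statistical power equal to 80% to detect 1 standard deviation change in these markers following treatment".

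**The concern.** There are two separate faults.

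1. Six plus four is 10, not 12. The study team cannot tell when the second stage closes, or which denominator belongs to the three-event boundary.
2. Rejection at the interim is one of the two ways to declare the product too toxic. The overall probability therefore cannot be smaller than the first-stage probability, yet 1.2% is below 11.4% and 62% is below 76.7%.

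Toxicity is the primary outcome, and these are the only operating characteristics given for its decision rule. A reader who relies on the figure labelled overall would think that a product with a 10% toxicity rate is wrongly rejected about once in 80 trials (1/0.012 = 83). The reader would also think that a 40% rate is detected less often than the rule actually detects it.

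**Working it through.** **Inputs** (sections 5.1, 11.3.2, 11.4): first stage n₁ = 6, stop if more than 1 toxicity; second stage n₂ = 4 as written, or 6 if the total is 12; declare too toxic if more than 3 toxicities in all; true rates p = 0.10 and 0.40. All toxicity results are exact binomial.

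**Step 1: the plan's first-stage figures.** P(X₁ > 1) = 1 − (1−p)⁶ − 6p(1−p)⁵.
- p = 0.10: 1 − 0.5314 − 0.3543 = 0.1143
- p = 0.40: 1 − 0.0467 − 0.1866 = 0.7667

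Both reproduce the plan.

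**Step 2: the source of 1.2% and 62%.**

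| Probability of more than 3 toxicities | p = 10% | p = 40% |
|---|---|---|
| Stated in the plan | 1.2% | 62% |
| Single stage, n = 10 | 1.28% | 61.8% |
| Single stage, n = 12 | 2.56% | 77.5% |
| Given first stage passed, 6 + 4 | 0.15% | 14.8% |
| Given first stage passed, 6 + 6 | 0.71% | 40.0% |

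Only the single-stage n = 10 row matches. The 1.2% is 1.28% truncated, since rounding would give 1.3%; the 62% leaves little doubt. Reading the figures as conditional on passing the interim does not rescue them.

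**Step 3: the overall probability for the two-stage rule.**
Overall = P(X₁ > 1) + P(X₁ = 0)·P(Y > 3) + P(X₁ = 1)·P(Y > 2), with Y binomial(n₂, p).

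- 6 + 4, p = 0.10: 0.1143 + 0.5314 × 0.0001 + 0.3543 × 0.0037 = 0.1156
- 6 + 4, p = 0.40: 0.7667 + 0.0467 × 0.0256 + 0.1866 × 0.1792 = 0.8014
- 6 + 6, p = 0.10: 0.1143 + 0.5314 × 0.00127 + 0.3543 × 0.01585 = 0.1206
- 6 + 6, p = 0.40: 0.7667 + 0.0467 × 0.1792 + 0.1866 × 0.4557 = 0.8601

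**Step 4: size of the error in the overall figures.**
- At p = 10%: 11.6/1.2 = 9.7 and 12.1/1.2 = 10.1, about tenfold.
- At p = 40%: 80.1 − 62 = 18.1 and 86.0 − 62 = 24.0 percentage points.

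**Step 5: the other figures attached to 12 patients.**
- Observed rate: 3/12 = 25%; 3/10 = 30%.
- Power for a 1 SD change (paired t-test, two-sided 0.05, noncentral t, SD taken as that of the paired change): 80.3% at n = 10 and 88.3% at n = 12. With 12 patients, 80% power corresponds to 0.89 SD.
- For the signed-rank alternative, simulation under normal data gives about 78% at n = 10 and 85% at n = 12.

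**The case against.** The strongest reply is that the plan does not hide the risk. The sentence just before the overall figures in 11.4.1 discloses the 11.4% and 76.7% chances of early rejection. The correct overall values lie only 0.1 to 0.6 points above the first of these (11.56 or 12.06 against 11.43) and 3.5 to 9.3 points above the second (80.14 or 86.01 against 76.67). That is fair. The tenfold understatement belongs to the figure labelled overall, and a careful reader would see that the two sentences conflict. But a plan that gives two incompatible probabilities for its primary decision still has to be corrected.

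Three narrower points also stand:

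- Section 11.3.2 does not call its figures overall. The error there is the use of n = 10 values for 12 patients. The failure to count the interim stop lies in 11.4.1.
- The 30% and the 80% are not independent mistakes. Both are right for 10 patients and wrong only beside the label 12. If 12 is correct, the stated power errs on the cautious side and concerns a secondary objective.
- The plan does not say whether the standard deviation is that of the change or of the marker. If it is that of the marker, power depends on the correlation between pre- and post-treatment values, which is not given. Assuming correlations from 0 to 0.75, power at n = 12 runs from 61% to 99%.

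Reading 12 as a mere ceiling does not resolve the conflict, because 5.1.3 calls it the total and the boundary uses it as the denominator.

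**Conclusion.** The concern holds. The enrolment arithmetic contradicts itself in the synopsis, 5.1.3 and 11.3.2. The overall probabilities in 11.4.1 are impossible beside the early-stopping probabilities in the same paragraph. The true chance of declaring the product too toxic is 11.6% or 12.1% at a 10% toxicity rate, and 80.1% or 86.0% at a 40% rate, for totals of 10 and 12 respectively; the plan states 1.2% and 62%. The first-stage figures are correct. The toxicity results assume only independent patients with a common toxicity rate and the stopping rule as written. The power figures also assume that 1 SD means the SD of the paired change. The documents do not settle which total is intended. This must be fixed, because it concerns the primary safety rule.

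**What to change.** Choose one total and use it in the synopsis, 5.1.3, 11.2, 11.3.2 and 11.4. The choice is the sponsor's; the figures that go with each are:

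| Item | Total 10 | Total 12 |
|---|---|---|
| Patients added after the first six | 4 | 6 |
| Final boundary | more than 3/10 | more than 3/12 |
| Highest tolerated observed rate | 30% | 25% |
| Overall rejection at 10% / 40% | 11.6% / 80.1% | 12.1% / 86.0% |
| Paired-t power, 1 SD of the change | 80% | 88% |

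In either case, define the overall probability as the chance of stopping at the first stage plus the chance of passing it and then exceeding the final boundary. Keep the first-stage figures. Beside the power figure, state which standard deviation is meant and which test it assumes.

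The cost is a wording amendment. It needs no patients beyond the stated maximum of 12. The stated false-rejection figure becomes less favourable, and the stated chance of detecting a 40% toxicity rate becomes more favourable.
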